5.1 Background

Singleton pregnancies

Preeclampsia (PE) which results in premature birth is a serious complication of pregnancy and a major cause of short and long-term maternal and perinatal morbidity and mortality (Witlin et al., 2000, Irgens et al., 2001, von Dadelszen et al., 2003, Yu et al., 2008). Extensive research in the last decade has resulted in the development of a method for first-trimester prediction of subsequent development of PE in singleton pregnancies from a combination of maternal characteristics and medical history with uterine artery pulsatility index (UtA-PI), mean arterial pressure (MAP) and serum placental growth factor (PLGF); with this method we can predict about 90% of early-PE with delivery at <32 weeks' gestation and 75% of preterm-PE with delivery at <37 weeks, at screen positive rate (SPR) of 10% (Wright et al., 2015, O'Gorman et al., 2016).

A subsequent multicentre trial using this algorithm found that prophylactic use of aspirin (150 mg / day from 11-14 until 36 weeks' gestation) reduces the incidence of early-PE by 89% and preterm-PE by 62% (Rolnik et al., 2017). A systematic review and meta-analysis on the prophylactic use of aspirin involving 18,907 pregnancies reported that administration of aspirin in women at high-risk of developing PE was associated with a significant reduction in the risk of preterm-PE (relative risk 0.62, 95% CI 0.45 to 0.87), but there was no significant effect on term-PE (RR: 0.92, 95% CI 0.70 to 1.21) (Roberge et al., 2018). The reduction in preterm-PE was confined to the subgroup in which aspirin was initiated at \leq 16 weeks' gestation and at a daily dose of \geq 100 mg (RR: 0.33, 95% CI 0.19 to 0.57) (Roberge et al., 2018).

Twin pregnancies

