Twins account for 3-4% of all births and over the last two decades the rate of twin pregnancies has increased steadily essentially due to two reasons: first, widespread use of assisted reproductive techniques and ovulation medications, and second, the increasing age of women when they conceive (Heino et al., 2016). In twin pregnancies, the rate of PE is about 9%, which is 3-times higher than in singleton pregnancies. However, twins are delivered at an earlier gestational age than singletons and consequently comparison of the overall rates of PE between twin and singleton pregnancies underestimates the relative risk of preterm-PE in twins which is 9-times higher (Francisco et al., 2017a, Francisco et al., 2017b, Fox et al., 2014). The same model for first-trimester prediction of PE developed in singleton pregnancies has been adapted for screening in twins; however, screening in a mixed population of singleton and twin pregnancies has demonstrated that use of risk cut-off resulting in SPR of 10% in singletons would result in SPR of 75% in twins with detection rates of about 75% for singletons and 99% for twins (Francisco et al., 2017b). In this respect all twin pregnancies can be considered to be at high-risk of preterm-PE and therefore in any potentially preventative intervention study all twins can be included.

A systematic review on the prophylactic use of aspirin in multiple pregnancies identified five trials. Use of aspirin was not associated with reduction in the incidence of PE in any of the trials but a meta-analysis of the trials, in a combined total of 898 pregnancies, reported that first, aspirin reduced the incidence of mild-PE (RR 0.44, 95% CI 0.24 to 0.82) but not severe-PE (RR 1.02, 95% CI 0.61 to 1.72), and second, there was significant reduction in PE if aspirin was initiated >16 weeks' gestation (RR 0.64, 95% CI 0.43 to 0.96) but not <16 weeks (RR 0.86, 95% CI 0.41 to 1.81) (Bergeron et al., 2016). These results are inconsistent with findings in singleton pregnancies. The authors recommended that additional studies are required before recommending that low-dose aspirin should be initiated early in pregnancy for all multiple gestations.

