6.5 Outcomes

Primary Outcome

To determine if the prophylactic use of low-dose aspirin from the first-trimester of pregnancy in women with twin pregnancy can reduce the incidence of PE with delivery <37 weeks' gestation.

PE will be defined as per the American College of Obstetricians and Gynecologists (ACOG 2013). The systolic blood pressure should be \geq 140 mm Hg and / or the diastolic should be \geq 90 mm Hg on at least two occasions four hours apart developing \geq 20 weeks' gestation in previously normotensive women (blood pressure <140/90 mm Hg) accompanied by one or more of the following new onset conditions at \geq 20 weeks' gestation:

- Proteinuria defined as ≥300mg in 24 hours or urinary creatinine ratio ≥30mg/mmol (0.3mg/mg) or two readings of at least ++ on dipstick analysis of midstream or catheter urine specimens if no 24hour collection is available.
- 2. Maternal organ dysfunction defined as any one of the following:
 - a. acute kidney injury with creatinine >97 µmol/L (1.1 mg / dL)
 - b. liver involvement with elevated transaminases (ALT or AST >90 IU/L or twice the normal concentration)
 - c. hematological complications (thrombocytopenia with platelet count <100,000/µL), disseminated intravascular coagulation or hemolysis.
 - d. neurological complications such as eclampsia, altered mental status, blindness, stroke, clonus, severe headaches, persistent visual scotomata

Secondary Outcomes

To determine the effect of low-dose aspirin on the incidence of (stratified according to chorionicity) :

- Delivery with PE at <32 weeks, <34 weeks, <37 weeks and at any gestation.
- Features of severe PE including:
 - o stroke
 - o Eclamspia
 - $\circ~$ systolic blood pressure >160 mmHg on at least one occasion
 - $\circ~$ diastolic blood pressure >110 mmHg on at least one occasion
 - \circ $\;$ respiratory failure requiring intubation or mechanical ventilation
 - o myocardial ischemia or infarction
 - o pulmonary edema
 - hepatic dysfunction (INR >1.2 in the absence of DIC)
 - hepatic hematoma or rapture
 - platelet count <100 x 109/litre
 - abnormal liver function enzymes (ALT or AST >67 iu/litre)
 - o acute kidney injury
 - o creatinine >150 μmol/L
 - o cortical blindness
 - o retinal detachment
 - o transfusion of any blood products
 - HELLP syndrome
 - o placental abruption
 - \circ postpartum hemorrhage (defined as blood loss ≥1 L within the first 24 hours after birth)

- \circ intensive therapy or high-dependency unit admission

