GH will be defined as per the American College of Obstetricians and Gynecologists (ACOG 2013). The systolic blood pressure should be \geq 140 mm Hg and / or the diastolic should be \geq 90 mm Hg on at least two occasions four hours apart developing \geq 20 weeks' gestation in previously normotensive women (blood pressure <140/90 mm Hg) in the absence of proteinuria or maternal organ dysfunction.

Collection of pregnancy and neonatal outcomes

Data on pregnancy outcome will be collected from hospital maternity records or general practitioners. The obstetric records of participants with pre-existing or pregnancy-associated hypertension will be examined to determine if the condition was chronic hypertension, PE or GH.

In the event when the neonates are admitted to Special Care Baby Unit (SCBU) / Neonatal Intensive Care

Unit (NICU), additional neonatal outcomes will be collected from the discharge summary of SCBU / NICU.

Other secondary efficacy parameters will be assessed by the clinical team at the time of delivery and recorded in the participants' medical notes (all data is routine clinical practice) and will be transcribed into the trial CRF by the trial team.

6.6 Participant Timeline:

The trial procedures by visit

Routine screening visit (11⁺²-13⁺⁶ week of pregnancy or CRL 45-84 mm)

Recording of: demographic characteristics, medical and obstetric history and concomitant medications (including COVID-19 vaccination status)

- Measurements of: height, weight, blood pressure and UtA-PI according to FMF guidelines
- Ultrasound scan for: measurement of CRL and NT and examination of each fetus for major defects
- Pregnancy dating: from CRL of biggest twin
- Blood sample for storage for future research (only in centres with available facilities)
- Patients meeting eligibility criteria and agreeing to participate in the trial: Informed consent, randomisation, IMP dispensing and taking of the first tablet either at this visit or (for those that require further time to consider their options) in a subsequent randomization visit up to 14⁺³ weeks

Randomisation visit (11⁺²-14⁺³ week of pregnancy)

- Informed consent, randomisation, IMP dispensing and taking of the first tablet
- This visit could be the same as the routine screening visit above

Follow up visits

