6.9 Assignment of intervention

Sequence generation: Randomisation will be by random permuted blocks and participants will be stratified by centre and chorionicity. The treatment allocation will only be revealed to the researchers after completion of the study or where clinically essential.

Allocation concealment mechanism: Each treatment pack will only be identified by a kit code. When a participant enrols onto the study, the randomisation system will assign participants two kit codes corresponding to the treatment arm to which they have been assigned. If IMP is being dispensed from a pharmacy, the participant or a member of the clinical team, on behalf of the participant, will bring the prescription with the allocated kit codes detailed to the pharmacy, where the pharmacy will provide her with the bottles matched to the kit codes. Neither the pharmacy at each clinical site or the clinical staff will have access to the codes, except in case of an emergency.

Allocation Implementation: Responsibility for who is enrolled in the trial and receives IMP is the Principal Investigator's (PI). S/he makes his/her eligibility decision according to the approved protocol. Other physicians, employed at the same Clinical Site may enrol participants as long as they appear on the Trial Delegation log and are signed off by the PI.

Blinding

RenaClinical will provide labelling for the IMP bottles ensuring complete blinding of the IMP to all investigators and participants in the study. That includes the PI, participating research doctors, pharmacists at the local clinical trial pharmacy, project managers and others involved in the trial. They are all blinded to the allocation. As mentioned previously, the tablets will be identical, so it will not be possible to distinguish between the active (aspirin) and placebo. RenaClinical and Sealed Envelope will keep the kit codes confidential to maintain the blind.

Emergency unblinding

In case of emergency, the facility to unblind a participant's treatment allocation will be available at all times during the study via an online service provided by Sealed Envelope, which has a telephone unblinding backup system in cases where the hospital network is not functioning. The coordinating team will receive an email informing them a participant has been unblinded but this email will not reveal the treatment allocation.

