6.10 Data collection, management and analysis

Data collection

All of the main participant information for this study will be entered into an electronic CRF that will be printed and signed by the enrolling researcher. The CRF will be composed of 3 parts:

CRF part 1 This will include participant demographics, medical and obstetric history, measurements of MAP and UtA-PI, performance of an ultrasound scan to confirm the gestational age by the measurement

of fetal CRL of the bigger twin, eligibility criteria, and randomization details. Participants will be identified on CRFs by participant code and site name, date of enrolment and the enrolling site-PI or fellow.

CRF part 2 This will record details of the routine clinical visits (including ultrasound findings, MAP, IMP compliance and adverse events) and details of the telephone interviews.

CRF part 3 This will record details of pregnancy and postnatal outcomes.

All parts of CRFs should be signed by the site-PI and / or fellows for each participant enrolled, including those removed / withdrawn from the study for any reason. The reason for removal/withdrawal must be noted on the study conclusion CRF by the site-PI. CRFs must be kept current to reflect the participant's status at each phase during the course of the study.

The CRFs will be the source documents of the study that must be available at all times for inspection by the regulatory authorities. A participant identification record will be kept by each site-PI that would allow linking of the participant study number, participant name and date of birth for those included in the study along with participant contact information. This file will be kept electronically at sites.

Ancillary CRFs

Ancillary CRFs, including exceptions to SAEs, SAEs and study exit forms will be available within the Sealed Envelope/Red Pill system. These should be completed, as required. If an SAE form is completed, the participating site must also email FFIS/FMF immediately following completion of the eCRF to alert them that an SAE form has been submitted so that a clinical review can be completed.

Non-adherence and non-retention

For non-adherers (as defined by poor attendance to clinical visits) we will record details of pregnancy and postnatal outcomes as for adherers. Reasons for non-adherence and non-retention and those lost to follow up will be recorded in the CRF.

Data management

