The Chief Investigators will act as custodian for the trial data. The following guidelines will be strictly adhered to:

- Participant data will be pseudo-anonymised.
- All pseudo-anonymised data will be stored on GDPR-compliant servers and/or a password-protected computer.

Statistical methods

Statistical analysis plan: A stand-alone Statistical Analysis Plan (SAP) detailing the analysis will be produced before follow up is complete. To ensure that the analysis can be validated and is reproducible, this document will include listings of all program code used for the statistical analysis together with sample outputs, tables and figures. The SAP may be informed by analyses of data blinded to treatment, but it will be finalised before the blind is broken. The SAP will be approved by the IDMC and by the TSC.

Results will be reported according to the CONSORT statement (Moher et al., 2001). It is envisaged that the analysis will be undertaken using R and WinBugs software.

Summary statistics will be produced for aspirin and placebo groups. Continuous data will be summarized in terms of means, standard deviations, minimum, maximum and quartiles. Attribute data will be summarised in terms of frequency counts and proportions.

Statistical analyses will be performed on an intention-to-treat basis. Logistic regression analysis will be used to determine the significance of difference in incidence of preterm-PE between the aspirin and placebo

groups, adjusting for the effect of centre (random effect) and the logistic transformation of risk. The treatment effect will be quantified as odds ratio with 95% confidence interval (CI) in the aspirin group. Homogeneity of the treatment effect will be examined by centre, chorionicity, risk group and specific maternal characteristics. Sensitivity analysis will be performed to examine the effect of withdrawal of consent and loss to follow up. Kaplan-Meier estimates of the cumulative incidence of PE by treatment group, in which deliveries without PE are treated as censored observations, will be produced. The statistical software package R will be used for data analysis. Results will be presented as 95% confidence intervals with no corrections for multiple testing.

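### The primary logistic model omits chorionicity, one of the two factors that stratify the randomisation; adding it is free, and the expected gain is small

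*Protocol*

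**What the plan says.** Section 6.9 of the protocol sets the allocation: "Randomisation will be by random permuted blocks and participants will be stratified by centre and chorionicity".

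Section 6.10, under statistical methods, uses logistic regression to test the difference in preterm preeclampsia between the arms, "adjusting for the effect of centre (random effect) and the logistic transformation of risk". The treatment effect is reported as an odds ratio with a 95% confidence interval.

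Chorionicity appears in two other places in the analysis:

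- Section 6.10, as a factor for heterogeneity: "Homogeneity of the treatment effect will be examined by centre, chorionicity, risk group and specific maternal characteristics".
- Section 6.5, in the lead-in to the secondary outcomes: "To determine the effect of low-dose aspirin on the incidence of (stratified according to chorionicity". The first item in that list is delivery with preeclampsia at several gestational cut-offs, one of which is 37 weeks. That is the primary event again. Sections 1.3 and 5.3 repeat this arrangement.

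Sections 5.4 and 6.3 place the determination of chorionicity at the routine first-trimester scan, before randomisation.

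**The concern.** When randomisation is stratified, the usual practice is to adjust the primary analysis for the stratification factors. Balance is forced within strata. An analysis that ignores a prognostic stratum counts as chance variation something the design has already removed, so its model-based standard error does not quite correspond to the design, and a baseline covariate that costs nothing goes unused.

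Here one stratum is kept and the other dropped without explanation. The protocol also treats the same event in two ways: delivery with preeclampsia before 37 weeks is broken down by chorionicity in the secondary list, but its primary test makes no adjustment for chorionicity. What is at stake is the coherence of the pre-specified model and a little precision.

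**Working it through.** **1. The two lists of factors side by side (protocol 6.9 and 6.10).**

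| Factor | Stratifies randomisation | In primary model | Elsewhere in the analysis |
|---|---|---|---|
| Centre | yes | yes, random effect | homogeneity |
| Chorionicity | yes | no | homogeneity; secondary outcomes |
| Risk (logit) | no | yes | homogeneity by risk group |

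**2. The plan's own sample size.** Inputs from section 6.7: 5.5% against 2.75%, two-sided 5%, 90% power. Allocation of 1:1 is assumed, because the protocol names two arms but gives no ratio. With p̄ = 0.04125,

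n per arm = [1.960 × √(2 × 0.04125 × 0.95875) + 1.2816 × √(0.055 × 0.945 + 0.0275 × 0.9725)]² / 0.0275² = 1,097,

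which is 2,194 in total against the stated 2,200. Power at 1,100 per arm is 90.1%. The stated figure reproduces. It is an unadjusted comparison of two proportions, so it depends on neither chorionicity nor risk and does not change with this point.

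**3. What omitting chorionicity does.** Trials of 2,200 women were simulated with 1:1 balance within chorionicity and a 5.5% event rate on placebo. The treatment odds ratio was (0.0275/0.9725)/(0.055/0.945) = 0.486. Each trial was analysed by logistic regression without and with a chorionicity term, with 3,000 trials per scenario and no centre or risk term. The protocol gives neither the monochorionic share nor the prognostic strength of chorionicity, so both are assumptions.

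With a 20% monochorionic share:

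| Chorionicity odds ratio | Type I error, without / with | Power, without / with |
|---|---|---|
| 0.5 | 0.050 / 0.050 | 0.908 / 0.908 |
| 1 | 0.053 / 0.053 | 0.915 / 0.915 |
| 2 | 0.050 / 0.051 | 0.910 / 0.910 |
| 3 | 0.045 / 0.048 | 0.897 / 0.899 |

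A separate run at a chorionicity odds ratio of 3 gave power of 0.900 without and 0.902 with the term at a 20% share, and 0.898 without and 0.901 with it at a 30% share.

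One entry has a simulation standard error of about √(0.9 × 0.1/3,000) = 0.0055 for power and √(0.05 × 0.95/3,000) = 0.0040 for type I error. Differences between rows are therefore largely noise. The useful comparison is within a row, where both models are fitted to the same data. The within-row change in power is 0 to 0.3 points.

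**4. The estimate itself.** At a chorionicity odds ratio of 3 the average treatment odds ratio was 0.4875 without the term and 0.4831 with it, a shift of 0.0044. This was the largest shift in the scenarios run.

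**5. Why the effect is small.** The design expects about 1,100 × 0.055 + 1,100 × 0.0275 = 60.5 + 30.25, or roughly 91 events. With so few events, the noise in the event count dominates the standard error. Allocation is already balanced on chorionicity, so the term has no imbalance left to correct.

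**The case against.** **The effect is negligible.** Type I error is about 5% either way, power moves by at most 0.3 points, centre is already in the model, and chorionicity-specific results for the primary event are planned through the homogeneity analysis and the stratified secondary outcomes. All of this stands, and it limits the point to a minor one. It does not remove it: a homogeneity test and a stratified secondary listing are not the primary test, and the primary test is where the design and the model part company.

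**The SAP may settle it.** It may, and it is not available here. But the protocol does not leave the covariates open. It names them, and the set it names leaves out a stratification factor.

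**A stronger reading of the risk covariate.** A reader might infer that the covariate cannot be computed. Section 5.1 describes a risk algorithm that uses uterine artery pulsatility index with "mean arterial pressure (MAP) and serum placental growth factor (PLGF"), and says of twins that "The same model for first-trimester prediction of PE developed in singleton pregnancies has been adapted for screening in twins". Placental growth factor is not among the scheduled measurements, so one might go on to predict loss of women, and of power, from the primary analysis. The protocol does not support this. Section 6.10 never ties risk to that marker. The sentence in section 5.1 also cites a model whose title in the reference list names maternal characteristics and medical history. CRF part 1 records "participant demographics, medical and obstetric history, measurements of MAP and UtA-PI", so a baseline risk can be built from planned data. Nothing in the protocol specifies a complete-case analysis, and any figure for lost power would rest on an invented missing fraction. The choice of algorithm and the handling of missing inputs are ordinary SAP content, and section 6.10 has the SAP finalised before unblinding.

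**Conclusion.** The point holds as a minor one. The primary model in section 6.10 leaves out chorionicity although section 6.9 stratifies on it. In the scenarios examined, including it is worth 0 to 0.3 points of power, with type I error at about 5% in both models and a shift of less than 0.005 in the treatment odds ratio.

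These sizes assume a monochorionic share of 20% to 30%, a chorionicity odds ratio between 0.5 and 3, 1:1 allocation, and no centre or risk terms in the simulated models. If the risk score already reflects chorionicity, which the protocol does not say, the gain would be smaller still.

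It should not be inferred that the planned test is invalid, that the estimate is materially biased, or that the sample size must change. The reason for the change is that the analysis should follow the randomisation.

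**What to change.** In section 6.10, state the primary model as treatment, chorionicity as a fixed effect, centre as a random effect, and the logit of risk. If the SAP already includes chorionicity, bring the protocol sentence into line with it. As a side note only, the SAP should compute risk from inputs recorded in CRF part 1.

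The cost is one sentence, one extra model parameter, and no new data, visits or participants. Section 7 lists changes to analyses among substantial amendments that go to ethics committees and competent authorities. Since the gain is small, it is reasonable to make the change together with the next amendment, provided it is settled before the blind is broken.

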6.7 Sample size

The sample-size calculation presented here is based on detecting a treatment effect that produces a 50% reduction in the incidence of preterm PE from an anticipated 5.5% in the placebo group to 2.75% in the aspirin group. A total sample of 2,200 participants has 90% power of detecting this difference at a (two-tailed) significance level of 5%. Allowing for 9% attrition, it will be necessary to randomise a total of 2,400 pregnancies. On the assumption that 60% of women with twin pregnancies fulfilling the entry criteria agree to participate in the study, we would need to approach 4,000 such women.

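### The planned Kaplan-Meier curves censor deliveries without preeclampsia, so they are not cumulative incidence and will overstate absolute risk and absolute benefit

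*Protocol*

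**What the plan says.** Section 6.10 of the protocol, under Statistical methods, fixes the estimator, the name given to it and the censoring rule in one sentence: "Kaplan-Meier estimates of the cumulative incidence of PE by treatment group, in which deliveries without PE are treated as censored observations, will be produced". It does not describe the curve as a hypothetical risk, and it plans no competing-risks estimator for it.

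The other PE analyses are on the plain incidence scale. The primary outcome in section 6.5 asks whether aspirin can "reduce the incidence of PE with delivery <37 weeks" of gestation. Section 6.10 analyses it this way: "Logistic regression analysis will be used to determine the significance of difference in incidence of preterm-PE between the aspirin and placebo" groups, and "The treatment effect will be quantified as odds ratio with 95% confidence interval (CI) in the aspirin group". The secondary outcomes in 6.5 include delivery with PE before 32, 34 and 37 weeks and at any gestation. They also include birth before 32, 34 and 37 weeks, split into spontaneous and iatrogenic. Section 5.1 observes that "twins are delivered at an earlier gestational age than singletons and consequently comparison of the overall rates of PE" between the two kinds of pregnancy understates the relative risk of preterm PE in twins.

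**The concern.** The name and the censoring rule do not fit together. Censoring means that the event could still happen after observation stops. After delivery without PE, delivery with PE cannot happen. Kaplan-Meier nevertheless treats these women as if they would go on to have the same PE risk as women still pregnant, and so assigns them PE events that cannot occur. The logistic model instead keeps them in the denominator as women without the outcome.

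A reader will compare a curve called cumulative incidence, at 32, 34 and 37 weeks, with the proportions reported for the same outcomes. The two will not match. The curve will show a higher PE risk in both arms and a larger absolute benefit than the trial observed. Twins deliver early, so many women would be censored before 37 weeks. Birth timing is itself a secondary outcome, so the independence that the hypothetical reading needs cannot be taken for granted.

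**Working it through.** **Inputs**
- PE with delivery before 37 weeks, section 6.7: "from an anticipated 5.5% in the placebo group to 2.75% in the aspirin group". Call this p.
- Share of all deliveries before 37 weeks, F: not in the protocol. Assumed 40%, 50% or 60% in the placebo arm.
- Two equal arms, no other loss to follow-up, and delivery with PE as the event: assumed.

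**The plan's own figure.** Two proportions, pooled variance, two-sided 5%, 90% power:

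n per arm = [1.960 × √(2 × 0.04125 × 0.95875) + 1.282 × √(0.055 × 0.945 + 0.0275 × 0.9725)]² / 0.0275² = 1,097, or 2,194 in total, against the stated 2,200.

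The design figures of 5.5% and 2.75% are therefore plain proportions, with deliveries without PE in the denominator.

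**Formula.** Suppose PE deliveries are a constant fraction p/F of all deliveries at each gestation. The cumulative hazard of any delivery to 37 weeks is -ln(1-F), and the PE part is p/F of that. Hence

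- 1-KM at 37 weeks = 1 - (1-F)^(p/F)
- Aalen-Johansen at 37 weeks = p

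**Results.** The share of deliveries without PE (F - 0.055) is the same in both arms. In the aspirin arm F is that share plus 0.0275.

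| All births <37 weeks (placebo) | Births without PE <37 weeks | 1-KM placebo | 1-KM aspirin | Difference (points) | Risk ratio |
|---|---|---|---|---|---|
| 40% | 34.5% | 6.8% | 3.4% | 3.4 | 0.499 |
| 50% | 44.5% | 7.3% | 3.7% | 3.7 | 0.498 |
| 60% | 54.5% | 8.1% | 4.0% | 4.1 | 0.496 |
| Aalen-Johansen, any F | any | 5.5% | 2.75% | 2.75 | 0.500 |

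Worked line at 50%: placebo 1 - 0.5^(0.055/0.5) = 0.0734; aspirin 1 - 0.5275^(0.0275/0.4725) = 0.0365.

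A day-by-day model with the same 40-60% gives 6.9%, 7.5% and 8.2%, so the placebo range is about 6.8-8.2%, or roughly 1.2 to 1.5 times 5.5%.

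**Other timing.** A daily grid from 22+0 to 36+6 weeks was run with 30-60% of women delivering *without PE* before 37 weeks and several timing shapes. It gives 6.0-10.2% (placebo) and 3.0-5.1% (aspirin). With 20-70%, placebo is 5.8-12.2%. The low end arises when PE deliveries come earlier than the others, the high end when they come later. Simulation with 1,100 per arm and 50% delivering without PE gave means of 7.6% and 3.8%. Every scenario overstated.

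**Relative effect.** Across these scenarios the risk ratio read from the curves is 0.49-0.52. This includes the case in which averted PE deliveries become other preterm births. The design odds ratio is (0.0275/0.9725)/(0.055/0.945) = 0.486; in the 50% row the curves give 0.479.

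**If aspirin changes other deliveries.** Two cases need separating.
- Equal observed PE (5.5% in both arms), with 50% against 40% delivering without PE: 1-KM is 1 - 0.445^(0.055/0.555) = 7.7% against 1 - 0.545^(0.055/0.455) = 7.1%. The Kaplan-Meier curves separate; the Aalen-Johansen curves agree at 37 weeks.
- Equal PE hazard, starting from the 50% row, with the hazard of other delivery cut by 20% in one arm: the PE cumulative hazard stays at 0.0762 and the other falls from 0.6169 to 0.4935. 1-KM is 7.3% in both arms. Aalen-Johansen is 5.5% against (1 - e^(-0.5698)) × 0.0762/0.5698 = 5.8%.

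**The case against.** The strongest reply is that the display is deliberate. The protocol states the censoring rule openly, and section 5.1 argues that early delivery hides PE risk in twins. Someone who holds that view may want the risk with other deliveries set aside. That is a legitimate quantity, and this stands. But it is not cumulative incidence, and its independence assumption is not stated. The wording would need correcting even if the estimator were kept.

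It also stands that the curves are descriptive. No test, error rate or sample-size figure depends on them. The statistical analysis plan, not shown here, may refine the figures, but the protocol sentence would still call for a mislabelled curve.

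Three stronger readings are tempting, and the documents do not support them.
- A reader might infer that the curves will contradict the primary result. That result is an odds ratio, and the relative effect read from the curves is almost the same. The conflict is in absolute risk and risk difference.
- A reader might infer that a difference in other preterm births would always separate the Kaplan-Meier curves spuriously. That holds when observed PE incidence is equal. When the PE hazard is equal and other deliveries are independent of it, the Kaplan-Meier curves coincide and the Aalen-Johansen curves separate.
- A reader might attach a specific multiple to the curves after 37 weeks. The overstatement does grow there, as few women remain pregnant, but any figure needs a distribution of term deliveries that the protocol does not give.

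**Conclusion.** The point holds as a mismatch between estimator and label with a real effect on absolute figures. Followed as written, the plan yields curves that lie above the observed incidence of delivery with PE in both arms and exaggerate the absolute benefit. With 40-60% of all deliveries before 37 weeks, the placebo curve reads about 6.8-8.2% against 5.5%. In the closed-form calculation the risk difference reads 3.4-4.1 points against 2.75. The direction follows from the censoring rule whenever deliveries without PE precede some PE deliveries. The size rests on the assumed share and timing of preterm birth. The relative effect is nearly unchanged unless aspirin alters when women deliver without PE. The primary analysis is not affected. The sentence should be corrected, but the trial's main conclusion does not turn on it.

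**What to change.** Replace the sentence in section 6.10 with a plan for Aalen-Johansen estimates of the cumulative incidence of delivery with PE, by gestational age and arm, taking delivery without PE (including pregnancy loss) as the competing event. Report the values at 32, 34 and 37 weeks with confidence intervals. With no other censoring they equal the observed proportions for the matching outcomes.

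If the Kaplan-Meier display is also wanted, describe it as the hypothetical risk of PE in the absence of other deliveries, state that it assumes those deliveries are independent of PE risk, and do not call it cumulative incidence.

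The cost is one or two sentences of analysis text. The estimator is standard in R, which the protocol already names, and no further data are needed. The change can be made before the analysis plan is finalised and the blind is broken.
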